11.5.1	Success Rates – Two Designs versus One Design	20
11.5.2	Success Rates – Actual versus Theoretical	20
11.5.3	Fitting Characteristics – Actual versus Theoretical	20
11.5.4	Supplementary Analysis	20
11.6	Interim Analysis	20
12	POTENTIAL RISKS AND BENEFITS	20
13	GENERAL STUDY MANAGEMENT	21
13.1	Relevant Standards	21
13.2	Ethics Review	21
13.3	Protocol Deviations	21
13.4	Premature Termination of the Study	21
13.5	Source Documentation	21
13.6	Monitoring	22
13.7	Audits	22
13.8	Records Retention	22
13.9	Confidentiality and Publication	22
14	REFERENCES	22
APPENDIX 1	Template Adverse Event Form	23
APPENDIX 2	Template Sample Enrolment and Randomisation Logs	26
APPENDIX 3	Template Product Accountability Log	29
APPENDIX 4	Template Product Dispensing Foil Log	31
APPENDIX 5	Grading Scales & Measurement Instructions	33

An Evaluation of the Fitting Success Rate of Senofilcon A Soft Contact Lenses

(TRTN-501)

PERSONNEL AND FACILITIES

PRINCIPAL INVESTIGATOR: [name] PhD MPhil FCOptom DCLP

CO-INVESTIGATORS: [name] BSc MCOptom
[name] BSc

STUDY LOCATION: Visioncare Research Clinic have
[name]
[name]
Farnham
[name], UK
[contact]
[contact]

Aston University Optometry Clinic
[name]
[name].
[contact]

MEDICAL MONITOR: [name] PhD BSc FCOptom
Aston University Optometry Clinic
[name]
[name].
[contact]

BIostatistician: [name] MSc
Visioncare Research Ltd
[contact] [name]
Email: [contact]

An Evaluation of the Fitting Success Rate of Senofilcon A Soft Contact Lenses**(TRTN-501)****SYNOPSIS**

- TITLE:** An evaluation of the fitting success rate of senofilcon A soft contact lenses.
- STUDY OBJECTIVES:**
1. To compare the lens fitting success rates for three combinations of senofilcon A lens pairs when fitted to a population skewed to larger corneas.
 2. To compare the actual fitting success rates of senofilcon A lenses with theoretical values from the Young model.
 3. To compare the fitting characteristics of senofilcon A lenses (tightness, corneal overlap) with theoretical values from the Young model.
- STUDY DESIGN:** This will be an approx. 40-60 subject, one-day, double-masked, randomised, repeated measures study. Each subject will wear the three lens types bilaterally in random succession (Acuvue® OASYS® with HydraClear Plus™ in two base curves and Acuvue® 1-Day Oasys with HydraLuxe™ in one base curve). A total of six lenses will therefore be worn by each subject (3 per eye).
- HYPOTHESES:**
- i. The fitting success rate for a combination of two senofilcon A designs is greater than for a single design when fitted to a population skewed to larger corneas.
 - ii. The fitting success rates for senofilcon A designs are equivalent to those predicted by the Young model.
 - iii. The fitting characteristics (tightness, corneal overlap) for senofilcon A designs are equivalent to those predicted by the Young model.
- TEST PRODUCTS:** Both lens types are manufactured by JJVC, in senofilcon A material with 38% water content and a shrinkage factor (20→34°C) of 0.997. Both are available in powers -1.00 to -6.00D and are CE marked.
- Acuvue® 1-Day Oasys with HydraLuxe™ (8.50/14.3)
 - Acuvue® OASYS® with HydraClear Plus™ (8.40/14.0, 8.80/14.0)
- LENS CARE PRODUCTS:** Unpreserved saline for rinsing, e.g. Saufion saline.
- NO. SUBJECTS:** Approximately 40-60 subjects. An attempt will be made to include ~50% subjects who have an HVID >11.75mm or corneal diameter >13.75mm.
- STUDY POPULATION:** Volunteer subjects will be enrolled if they meet the baseline screening criteria and the inclusion and exclusion listed below. Ideally at least half of the eyes will fall within the top quartile of average corneal diameters ie >HVID 11.75mm or corneal diameter >13.75mm or will have demonstrated loose / tight fitting contact lenses in previous studies.

Inclusion Criteria:

- i. Age 18-70 years.
- ii. Able to read, comprehend and sign an informed consent.
- iii. Willing to comply with the wear and study assessment schedule.
- iv. Spherical distance prescription between -0.50 and -6.00 (inc.).
- v. Astigmatism, if present, ≤ 1.50 DC in both eyes.
- vi. Have normal eyes with no evidence of any ocular abnormality or disease. For the purposes of this study a normal eye is defined as one having:
 - A clear central cornea
 - No anterior segment disorders
 - No clinically significant slit lamp findings (i.e. corneal oedema, significant staining, central scarring, infiltrates, active neovascularisation)
 - No other active ocular disease (including pterygia)

Exclusion Criteria:

- i. Previous anterior ocular surgery
- ii. Any active corneal infection, injury or inflammation
- iii. Large pinguecula likely to affect soft lens fit
- iv. Systemic or ocular disease or medication which might interfere with CL wear
- v. Pregnancy or breastfeeding
- vi. Participation in any concurrent trial

NO. SITES:	Two sites in UK: Visioncare Research Ltd, Farnham; Aston Research Clinic, Birmingham
END POINTS:	Completion of assessment of three pairs of lenses or discontinuation.
VISITS/SCHEDULE:	One visit
PROCEDURE:	Lenses will be inserted and each pair assessed after ~30 minutes.
CLINICAL VARIABLES:	
Primary variables:
 
Lens fit: horizontal* & vertical* centration (mm), post-blink movement in primary gaze* (mm), version lag (mm), edge tightness (0-4), tightness (push-up %), horizontal corneal overlap (mm)*, diameter acceptance (mm), overall fit acceptability (0-5), fit success rate (%).
 
Corneal topography: Sim-K-readings and corneal shape factor (Medmont), horizontal HVID* (photo slit lamp) corneal sagittal height, corneal diameter (Visante OCT).
 
* From photographs / video

THEORETICAL FIT VARIABLES:	Edge strain (%), corneal overlap (mm), fit success (Yes/No) based on following criteria: Edge strain: 0-6%, Horizontal corneal overlap: 0.2-1.2mm.

1 INTRODUCTION

Since ocular topographies vary within the population,¹ it is important that contact lens designs are selected that comfortably and successfully fit a wide range of eyes. Multiple designs generally give a wider coverage of the population than single designs. Because soft contact lenses are generally not available in a wide range of parameters, it is difficult to evaluate the effectiveness of design combinations. However, senofilcon A lenses have recently become available in multiple diameters, which offers the opportunity to explore the utility of various design combinations.

Computer modelling provides useful insights into the relationship between lens design and fit and allows an estimation of the fitting success rate for a given lens design on a given population.^{2,3} Recent calculations suggest that a combination of multiple diameter designs is likely to be more successful than multiple base curves of identical lens diameter.⁴

The main purpose of this study is to evaluate the fitting success of various combinations of senofilcon A lens designs. A secondary purpose will be to evaluate the validity of the Young soft contact lens fit model.²

2 STUDY OBJECTIVES

- i. To compare the lens fitting success rates for three combinations of senofilcon A lens pairs when fitted to a population skewed to larger corneas.
- ii. To compare the actual fitting success rates of senofilcon A lenses with theoretical values from the Young model.²
- iii. To compare the fitting characteristics of senofilcon A lenses (tightness, corneal overlap) with theoretical values from the Young model.

2.1 Hypotheses

The following hypotheses will be tested:

- i. The fitting success rate for a combination of two senofilcon A designs is greater than for a single design when fitted to a population skewed to larger corneas.
- ii. The fitting success rates for senofilcon A designs are equivalent to those predicted by the Young model.
- iii. The fitting characteristics (tightness, corneal overlap) for senofilcon A designs are equivalent to those predicted by the Young model.

3 STUDY DESIGN & RATIONALE

This will be a one-day, double-masked, randomised, repeated measures study. Each subject will wear the three lens types (Acuvue® OASYS® with HydraClear Plus™ in two base curves and 1-Day Oasys with HydraLuxe™ in one base curve). A total of six lenses will therefore be worn by each subject (3 per eye).

An attempt will be made to include subjects who have large corneas or have previously demonstrated loose / tight fitting contact lenses since eyes with larger corneas tend to be less successful in contact lens fitting.

3.1 Randomisation

Subjects will wear each of the three lens types bilaterally in random succession. A random number generator (Microsoft Excel) will determine the randomisation of lenses to subjects, which is then incorporated into the Randomisation Log.

The randomised assignment of subjects will be performed at the first assessment prior to the first randomised lens fitting. The following must be ensured prior to randomisation:

- Informed consent has been obtained
- Subjects meet all inclusion / exclusion criteria
- Subject history and baseline information have been collected

Subjects who are discontinued may be replaced in order to achieve the targeted minimum number of cohort subjects, but the ID number will not be reused.

3.2 Masking

To prevent bias, subjects will be masked to lens type and lens codes, and investigators will be masked to lens code. An unmasked individual at Visioncare Research will be responsible for preparing the lenses by over-labelling with the appropriate code. The lenses will be coded (A, B or C) to facilitate masking.

4 INVESTIGATIONAL SITES

4.1 Number of Sites

Two investigational sites in the UK: Visioncare Research Clinic, Farnham: Aston University Research Clinic, Birmingham

4.2 Investigator Recruitment

The Investigators will be required to fulfil the following criteria:

- General Optical Council (GOC) registered optometrist
- At least two years post-registration contact lens fitting experience
- Experienced investigators trained in Good Clinical Practice (GCP)
- Willingness to follow the study protocol and to co-operate with the study monitors

5 STUDY POPULATION

5.1 Number of Subjects

Approx. 50 subjects (40-60 subjects) who fulfil the inclusion criteria will be fitted with study contact lenses.

In order to fully explore the hypothesis an attempt will be made to include subjects who have an HVID of >11.75mm, Corneal Diameter of >13.75mm, or who have exhibited 'loose' or 'tight' lens fittings in previous studies.

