11.1 Sample Size Rationale

A sample size of 60 subjects showing a 90% success rate would give an 80% confidence interval of $\pm 5.0\%$. This would statistically differentiate success rates of 85% and 95%.

A sample size of 60 is sufficient to detect a mean difference of 5 (0-100) in tightness, or 0.2 mm in corneal overlap assuming the standard deviation of the mean differences in Table 2 below and assuming $\alpha=0.05$ with a power of 95%.

Table 2: Sample Size Justification:

	Sample Size	
	Tightness (0-100)	Corneal overlap (mm)
Mean of paired difference	5	0.2
SD of paired difference	10	0.4
Minimum sample size per group	42	42

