11.3 Analysis Population

The primary hypotheses will be analysed on all randomized subjects who have successfully completed the study without a protocol deviation that is deemed to impact the assessment of the primary hypotheses (i.e. the per-protocol population).

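### Section 11.1 gives precision and 95% power only at 60 subjects, while Section 5.1 plans about 50 and allows 40; the sample-size table's minimum of 42 is itself too low for 95% power

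*Protocol*

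**What the plan says.** The synopsis gives the size as "Approximately 40-60 subjects". Section 5.1 adds a centre: "Approx. 50 subjects (40-60 subjects) who fulfil the inclusion criteria will be fitted with study contact lenses".

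Section 11.1 is written for the top of that range:

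- Precision: "A sample size of 60 subjects showing a 90% success rate would give an 80% confidence interval of" ±5.0%.
- Power: "A sample size of 60 is sufficient to detect a mean difference of 5 (0-100) in tightness, or 0.2 mm in corneal overlap", at a significance level of 0.05 and 95% power.
- The table in Section 11.1 (labelled Table 2, like the assessment schedule in Section 8.2.8) lists differences of 5 points and 0.2 mm, gives the "SD of paired difference" as 10 and 0.4, and states a minimum of 42 for both variables.

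Section 11.2 makes all tests two-sided. Section 11.3 analyses "all randomized subjects who have successfully completed the study" without a deviation judged to affect the primary hypotheses. Sections 3.1 and 5.6 permit, but do not require, replacement of discontinued subjects. Section 5.4 allots enrolment numbers 01 to 60 only, and they are not reused.

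**The concern.** The protocol describes one trial in Section 5.1 and justifies a larger one in Section 11.1. It gives no precision or power at 50, the number it expects to fit, or at 40, the number it permits. A trial that fits 40 complies with Section 5.1 yet falls below the minimum stated in Section 11.1.

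The two sections also count different things: Section 5.1 counts subjects fitted, while the analysis counts per-protocol completers. The minimum of 42 might reassure a reader that 50 is enough, so it matters whether 42 follows from the inputs printed above it.

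At stake is the accuracy of the stated sizing. A result from 40 to 50 subjects would be read against precision and power that it does not have.

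**Working it through.** **Inputs, all from the protocol.** Success rate 90% and 80% confidence (Section 11.1); differences of 5 points and 0.2 mm with SDs of 10 and 0.4 mm (Section 11.1 table); significance level 0.05 (Section 11.1), two-sided (Section 11.2); subject as the unit, as in Section 11.1. The standardised difference is 5/10 = 0.2/0.4 = 0.5 for both variables.

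**Formulas.**

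- Half-width = 1.2816 × √(0.9 × 0.1 / n).
- Power, paired t: noncentral t with n − 1 degrees of freedom and noncentrality 0.5√n.
- Power, normal approximation: Φ(0.5√n − 1.960).

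**The plan's figures at 60.** Half-width = 1.2816 × √(0.09/60) = 4.96%, which rounds to the stated ±5.0%. Power is 96.8% (t) or 97.2% (normal), so at least 95% is delivered. Both statements tied to 60 are correct.

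**Across the permitted range.**

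| Subjects analysed | 80% half-width | Power, paired t | Power, normal |
|---|---|---|---|
| 60 | ±4.96% | 96.8% | 97.2% |
| 54 | ±5.23% | 95.0% | 95.7% |
| 50 | ±5.44% | 93.4% | 94.2% |
| 42 | ±5.93% | 88.6% | 90.0% |
| 40 | ±6.08% | 86.9% | 88.5% |

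**Numbers needed for the stated targets.**

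- ±5.0% at 80% confidence: n = 1.2816² × 0.09 / 0.05² = 59.1, so 60.
- 95% power, normal: n = ((1.960 + 1.645)/0.5)² = 51.98, so 52. By paired t, 54.

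**The table's 42.** It does not follow from 95% power with a two-sided test. At 90% power the normal formula gives ((1.960 + 1.2816)/0.5)² = 42.03, so 42 looks like a 90% figure. A one-sided test at 95% power gives 44 (normal) or 45 (t). The protocol does not say how 42 was obtained, so its origin is an inference. That it falls short of 95% power on the printed inputs is not.

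**The case against.** Several points on the other side stand.

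- A reader might infer that the stated figures fail throughout 40 to 60. They do not. The 95% power holds from about 54 analysed subjects, and at 50 the loss is 1.6 points of power (95 − 93.4) and about 0.4 points of half-width. Power of 86.9% at 40 is still respectable.
- Sixty lies inside the planned range, so Section 11.1 does not describe an impossible trial. It does describe the best case: numbers are issued at consent, before eligibility is confirmed, and stop at 60. Analysing 60 would therefore need no ineligible enrolment, discontinuation or exclusion.
- A reader might assume that the analysed number must fall below the number fitted. The protocol gives no dropout rate, the trial is a single visit and replacement is allowed. A lower number is possible, not certain.
- A reader might also infer that an open final number invites stopping on results. Nothing links the final number to results: no interim analysis is planned (Section 11.6) and investigators are masked to lens code (Section 3.2).
- Both eyes are fitted, and Section 11.5.2 reports the proportion of eyes. With two eyes per subject the half-width is 1.2816 × √(0.09(1 + ρ)/(2n)), where ρ is the correlation between eyes. This stays within ±5.0% at 50 subjects for ρ up to about 0.69 (100/59.1 − 1), and at 40 for ρ up to about 0.35 (80/59.1 − 1). The protocol gives no correlation and Section 11.1 counts subjects, so this could become a justification but is not the one offered.

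The claim that 50 is safe because it exceeds 42 does not stand, because 42 does not deliver the stated power.

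**Conclusion.** The point holds for the lower part of the range. Section 11.1 is correct at 60, but its figures are not those of the trial in Section 5.1: ±5.4% and 93.4% power at 50, and ±6.1% and 86.9% at 40. The shortfall is minor at the planned centre and clear at the floor. Separately, 40 contradicts the stated minimum of 42, and 42 is 10 to 12 subjects short of the 52 to 54 that 95% power requires.

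These results rest on the protocol's assumed 90% success rate and 0.5 SD difference, a two-sided 5% level, and the subject as the unit. They do not show that the trial is badly underpowered or that its final size will be chosen on results; the documents support neither reading. This is a correction to the stated sizing and should be made.

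**What to change.** 1. In Section 11.1, give precision and power at the planned number (about 50) and at the lowest acceptable number (40), both counted as per-protocol completers.
2. In the Section 11.1 table, change the minimum to 52 (normal) or 54 (t) for 95% power, or keep 42 and state that it corresponds to about 89 to 90% power. Either way, the stated minimum and the permitted floor must agree.
3. In Section 5.1 and the synopsis, name one target number of completers, set before fitting starts. If that target is 60, extend the enrolment numbers in Section 5.4 beyond 60 so that ineligible or discontinued subjects can be replaced.

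The first two changes, and naming the target, are wording only. The cost is slightly less favourable stated power and precision; choosing 60 completers instead would mean some additional recruitment.

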5.2 Inclusion Criteria

All subjects must satisfy the following conditions prior to enrolling in the study:

- i. Age 18-70 years.
- ii. Able to read, comprehend and sign an informed consent.
- iii. Willing to comply with the wear and study assessment schedule.
- iv. Spherical distance contact lens requirement between -0.50 and -6.00 (inclusive).
- v. Astigmatism, if present, ≤ 1.50 DC in both eyes.
- vi. Have normal eyes with no evidence of any ocular abnormality or disease. For the purposes of this study a normal eye is defined as one having:
 - A clear central cornea
 - No anterior segment disorders
 - No clinically significant slit lamp findings (i.e. corneal oedema, staining, central scarring, infiltrates, active neovascularisation)
 - No other active ocular disease (including pterygia)

5.3 Exclusion Criteria

Any of the following will render a subject ineligible for inclusion:

- vii. Previous anterior ocular surgery
- viii. Any active corneal infection, injury or inflammation
- ix. Large pinguecula likely to affect soft lens fit
- x. Systemic or ocular disease or medication which might interfere with CL wear
- xi. Pregnancy or breastfeeding
- xii. Participation in any concurrent trial

5.4 Subject Identification

Subjects will be identified by a six-digit code made up of the site identifier (XX), the two-digit subject enrolment number (XX), and subject initials (XX). Enrolment numbers 01-30 will be assigned to Site 1, and numbers 31-60 will be assigned to Site 2.

The enrolment ID **must** be assigned to the subjects sequentially. Enrolment numbers will be in ascending order for each site. Thus, the first subject to be enrolled at Site 01 will be 01/01, the second 01/02 and so forth. The first subject to be enrolled at Site 2 will be 02/31, the second 02/32 and so on.

5.5 Study Withdrawal Criteria

Due to the nature and duration of the study, no circumstances are foreseen whereby this study would be prematurely terminated. However, if during the study it becomes evident to the Investigator that the study contact lenses pose a threat to subject well-being, the study will be terminated. The Research Ethics Committee (REC) will be advised of the reason for termination.

5.6 Subject Replacement

Subject IDs will not be reused should a subject drop-out or be discontinued from the study. If subjects are discontinued or drop out of the study, new subjects may be enrolled to ensure adequate subject numbers complete the study.

5.7 Subject Compliance

This is a one-day study and, therefore, there is little scope for subject non-compliance. However, subjects will be questioned at the follow-up assessments to check whether they have removed the lenses or failed to follow the instructions for any reason.

6 MATERIALS

6.1 Study Lenses

Table 1: Lens Details

	Acuvue® 1-Day Oasys with HydraLuxe™	Acuvue® OASYS® with Hydraclear Plus™
Manufacturer	JJVC	JJVC
Material/ water	senofilcon A	senofilcon A
Water content	38%	38%
Shrinkage factor (20→34°C)	0.997	0.997
Base curve (mm)	8.50	8.40, 8.80
Diameter (mm)	14.3	14.0
Powers (D)	-1.00 to -6.00	
	CE marked	

6.2 Trial Lens Fitting Sets

Lenses will be provided by the Investigator sites.

6.3 Lens Care Products and Other Study Products

Unpreserved saline for rinsing away fluorescein or for rinsing contact lenses, e.g. Sauflon saline.

6.4 Lens Preparation

An unmasked individual at Visioncare Research will be responsible for preparing the lenses by over-labelling with the appropriate code: A, B or C.

6.5 Lens Replacement Schedule

Subjects will wear a new pair of lenses for the duration of each 30-minute section of the study. Therefore, there is no requirement for subjects to replace their lenses. If subjects experience any complications with the study lenses, they should speak to the Investigator.

6.6 Product Accountability

Product Accountability and Dispensing Foil Logs will be kept by each site (Appendix 3 and 4). Number of lenses received (listed by power and lot number) and number of lenses used (even if not dispensed) will be recorded on these logs.

6.7 Study Document and Case Report Forms (CRFs)

The following forms will be completed where appropriate:

Investigator CRF Booklet:

- A) Baseline form
- B) Lens Assignment Form
- C) Follow Up Assessment form (including any Unscheduled Visits)
- D) Study Exit Form

Additional Forms

- A) Statement of Informed Consent
- B) Participant Information Sheet
- C) Eligibility Checklist (in Baseline CRF)
- D) Enrolment Log
- E) Randomisation Log
- F) Adverse Event Form
- G) Product Accountability Log
- H) Product Dispensing Foil Log

7 TREATMENT

7.1 Study Product Formulations

The contact lenses are CE marked and supplied sterile in single use blister packs containing buffered saline solution.

7.2 Device Administration

The single use devices will be used on a daily wear basis and disposed of after fitting and assessment on same study day.

8 METHODS AND ASSESSMENTS

8.1 Subject Recruitment

Recruitment materials (adverts, letters, etc.) must be approved by the Research Ethics Committee. The Investigator will provide an approved advert and letter for the recruitment purposes. Any changes to these must be submitted back to the ethics committee.

The procedures listed below will be conducted on all subjects. Variables must be collected in the order they are listed on the Case Report Form (CRF).

To participate in this clinical study, the Investigator will explain the Statement of Informed Consent to the subject, ensure each subject understands the Participant Information Guide and determine subject eligibility.

The Investigator is required to answer any questions the subject has concerning the study or the information contained in the Statement of Informed Consent and Participant Information Guide.

A subject is considered enrolled when he or she signs the Statement of Informed Consent.

